Under the provisions of the Patient Protection and Affordable Care Act (ACA), many more previously uninsured individuals will have access to healthcare coverage, including through Medicaid. While obtaining healthcare coverage can improve health outcomes,[1, 2] the newly insured still face challenges in using the healthcare system effectively and efficiently. They face challenges in finding and connecting with a primary care provider, and preventable hospitalizations and emergency department use has been found to increase, especially in Medicaid populations.[3-5] In addition, medically underserved minority and poor communities who historically have had limited access to health care services are largely unprepared to maximally benefit from evidence-based approaches to prevention and wellness. Many individuals and communities lack the necessary tools to prioritize their own health care needs, take advantage of these health services, or effectively participate in their own health decision making. For example, low health literacy has been found to be 3 to 5 times more common in minority populations, especially Hispanic adults.[6] Low health literacy is associated with increased hospitalizations and emergency room use, lower use of preventive measures (mammography, influenza vaccine), poorer ability to take medications appropriately, and poorer overall health status and higher mortality.[7-9] Recent immigrants less likely to have a usual source of care[10] and both Blacks and Hispanics are less likely than Whites to identify a doctor's office as their usual source of care.[11-14] Having a usual source of care, and especially a regular doctor,[15-17] is associated with better access to care,[15, 17, 18] and lower unmet needs,[17] and better utilization of preventive services[12, 16, 19-25] for both parents and their children.[26-28] Increasing community level capacity for effective and efficient healthcare utilization is essential to narrow the most pressing health disparities and achieve the Healthy People 2020 objectives.[29]

The stubborn health disparities that impact ethnically diverse and low-income populations are exacerbated by a complex array of social determinants and by fundamentally dysfunctional interactions with the health care system. Even after accounting for educational attainment, communication with health care providers is generally poor, and racial/ethnic and other linguistic minorities experience this phenomenon more acutely than white non-Hispanic individuals.[36] Racial, ethnic and gender discordance may also exacerbate the already uneven power dynamic that is inherent to the doctor-patient relationship. Furthermore, limited access to evidence-based health information that is tailored (in terms of gender, culture, language, and literacy level) to the needs of the individual effectively disenfranchises the communities that may have the most pressing health needs. In totality, these factors lead to generally low rates of participation in medical decision making and low levels of satisfaction among low-income and ethnic minority patients.[76] The proposed intervention is designed to address this problem by testing the effectiveness of community health workers trained according to a community-developed curriculum and functioning as personal educational and navigation aides to effectively empower

low-income women as consumers of the health care product, and in this way allowing them to take charge of their health.

II. OBJECTIVES

The overarching question addressed by this study is: Does access to a trained community health worker (CHW) improve newly enrolled Medicaid health plan members' engagement in the healthcare system? Specific research questions to be addressed by the proposed study include the following: 1) Does access to a CHW improve the likelihood of members identifying a primary care provider and completing a primary care intake visit during the year [primary outcome]; 2) Will the CHW intervention improve the use over the next year of each of the five reproductive preventive service recommendations made by USPSTF for women in this age group? 3) Will the CHW intervention lead over the next year to a decreased likelihood to use the emergency department and of preventable hospitalizations? 4) Does access to a CHW improve members' ability to make informed choices with regard to their use of the healthcare system and own health? 5) How many and what types of new Medicaid members take advantage of access to a CHW? 6) What resources are required to make these CHWs available to this population? Through our partnership with the University Family Care (UFC) health plan we will be able to perform subgroup analyses to explore differences by age group race/ethnicity, rural/urban, and border/non-border communities on both uptake (who chooses to use CHW services) and outcomes of the proposed intervention.

[figure not shown]
III. STUDY DESIGN

This project will use a mixed qualitative/quantitative pre/post study nested within a randomized controlled effectiveness trial. The intervention is conducted within the setting of a large regional Medicaid health plan that has a significant presence in southern Arizona. **The target population will be newly enrolled female health plan members between the ages of 18 and 39** who will be randomly selected to be invited to access a Community Health Worker (CHW) (the intervention arm), and those not selected will constitute the usual care control group. The University Family Care health care plan will provide the research team with a dedicated health plan analyst that will interface with the research team to set up the biased coin randomization process and procedures for the health plan claims data pulls, merges and de-identification, and the delivery of other member data including demographic characteristics, medical/pharmacy claims and member satisfaction surveys.

Once participants are randomized into the intervention arm they will be contacted by the Community Health Worker, who will be a University of Arizona employee, who will set up an individual confidential appointment with the potential participant. Appointment times and locations will be modified to meet the needs of the individual participant. Based on our experience, delivering CHW health education content, we anticipate that locations will vary and

include homes, health and community centers, schools, libraries, churches, supermarkets, as well as youth athletic events and neighborhood gatherings.

Study Schema

IV. STUDY ENROLLMENT

Study Population

Focus Group Participants

The first part of the project will recruit participants for a series of focus groups which will help finalize curriculum content and study surveys. A total of 30 participants will be recruited according to the following eligibility criteria:

- 1) Newly enroll members: University Family Care members who have recently enrolled in the health care plan. Less than 3 months from enrollment.
- 2) Previously enrolled and engaged: University Family Care members who are older enrollees (more than 3 months) and have had an appointment with their primary care physician.
- 3) Previously enrolled and not engaged: University Family Care members who are older enrollees (more than 3 months) and have not had any interaction with their family care provider.

Intervention Participants

Participants eligible for the intervention will include newly enrolled women in one of Arizona's state-wide Medicaid health plans (University Family Care) who are ambulatory and community-dwelling, and between the ages of 18-39.

Exclusion criteria includes: men, any women enrolled in the Medicaid plan that are not within our study's age range (18-39). We will not be actively recruiting pregnant women but if someone that is pregnant decides to participate, she will not be excluded from the study.

Recruitment Methods

Focus Group Recruitment

Recruitment will take place during the fall 2014 through spring 2015. Each focus group will range between 8 to 10 participants for a total of 30 participants in this component of the study. The purpose of the focus groups is to gather data in order to create questions to be used in the member satisfaction survey that will be administered with the potential participants in the next component of the study (e.g., the 1000 planned enrolled participants).

Participant recruitment will be facilitated by the University Family Care team who will identify potential participants and make the first study invitation. Since recruitment for focus group will be the first effort in reaching out to participant, UFC will start by testing 2 approaches for recruitment: 1) invitation by mail and 2) invitation by telephone. Once members agree to be in the study, referrals will be emailed to the program coordinator who will call the potential participant with more information about the study and dates for focus groups.

The study coordinator will use the following script to explain the project to participants. Depending on the primary language of the participant, the sample script for recruitment will be available in English or Spanish.

Sample Script for Recruitment for Focus Groups

Hello. You are invited to participate in a research study to learn about your thoughts about your use of health care services, any challenges you face in your health and obtaining healthcare, and how you would describe a successful interaction with your health care services provider.

We would like to interview a group of health plan participants and get your input. The benefits to you of doing this study are that you might learn some new things about yourself, your health care plan and you might enjoy sharing your ideas and feelings about accessing health services and limitations within the health services to health information. In addition, your participation in this study may help me and others better understand how to help women and families in our community navigate health care services and resources.

The research team and investigators will be the only people who know that you are participating in this study. Anytime I use the information you give me, I will always identify you with a fake name (if you would like, you can decide what name I use for you). When I interview you with a group of other health plan members, I would like your permission to record our interview and also take notes to remind me about what we talked about. I, my principal and co-investigators, and the research team will be the only ones who get to listen to these recordings. When I am not

using the recordings, they will be kept on a secure computer server that only we have access to. When I am not using the notes, they will be kept in a secure locked cabinet that only I have the key to. After I have finished with this study, all of these recordings will be kept on a secure locked cabinet for a time period required by The University of Arizona.

As part of your participation in this study, I will interview you with a group of 8 to 10 other health plan members about your use of the healthcare system, barriers/challenges you have encountered in obtaining healthcare and how you would describe a successful interaction with your health care provider. I have a few general questions I want to ask the group. If you want to share personal experiences, you may, but that is not expected. You will receive compensation for participating in this group interview.

The most important thing for you to remember while you are participating in this study with me is that there are no right or wrong answers to the questions I ask you. All I am looking for is your opinion or ideas or feelings, and if I ask you to tell me more, or explain your answer, it is because I want to be really sure I understand what you are telling me. Always remember that in this situation you are the expert, or teacher, and you are explaining to me what health resources are needed in your community.

You should also know that you can decide to not participate in this study, or stop doing it at any time after you have started—this is your decision. If you decide to stop doing this study, your decision will not affect any future contact you have with the University of Arizona.

An Institutional Review Board responsible for human subjects research at The University of Arizona reviewed this research project and found it to be acceptable, according to applicable state and federal regulations and University policies designed to protect the rights and welfare of participants in research.

Intervention recruitment

The intervention participants will be recruited monthly from the Arizona state-wide Medicaid health plan, University Family Care, newly enrolled women ages 18-39. Once members agree to be in the study, referrals will be emailed to the program coordinator who will forward the member's contact information to CHWs to call and schedule appointments. Potential participants will be called with detailed information about the study; overall purpose, benefits and what to expect if they decided to participate. This first phone call will also include a review and confirmation of study eligibility. If the participant agrees to be in the study, the CHW will schedule an appointment to conduct the 50 min face to face presentation. This first presentation will include 20 minutes for consent and baseline survey and 30 minutes for the educational content.

Sample Script for Recruitment for Intervention

Hello. You are invited to participate in a presentation by a community health worker, along with a short pre and post presentation survey, to learn about your satisfaction with services provided by the community health worker and your medical provider (s).

***The purpose** of the community health worker presentation is to provide you with knowledge about the appropriate reproductive health screening recommended for your age group and to share information about resources that are available to you through your health care plan.*

*We would like to get input from a large group of health plan members. **The benefits to you** of doing this study are that you might learn some new things about yourself, your health care plan's services and you might enjoy sharing your ideas and feelings about health topics and health resources.*

In addition, your participation in this study may help us better understand how to help women and families in our community navigate health care services and resources.

I, the principal and co-investigators, and the research team will be the only people who have access to your results of the pre and post surveys. All of the surveys and consent forms will be kept in separate locked cabinets. The project will also be asking for your permission in the form of signed a Protected Health Information for Research (PHI) to access to the following information from the University Family Care health plan: 1) Selection and use of a primary care provider; 2) Use of preventive services; and 3) Use of emergency and hospital services.

You will be asked to complete a 15 minute questionnaire at the beginning of the 30-minute Community Health Worker presentation. Booster telephone support calls will occur at 2 and 4 months after the Community Health Worker presentation to help you come up with questions you might want to ask your doctor specific to preventive services. At month 6, you will receive a call from a research team member to administer a 15 minute 6-month survey identical to the survey that was completed before the community health worker presentation. Compensation will be provided for your participation in the community health worker presentation.

We will provide presentations to 1000 participants each year for a total of three years. The most important thing for you to remember is that your participation in this study is completely voluntary. You should also know that you can decide to not participate in this study, or stop doing it at any time after you have started—this is your decision. If you decide to stop doing this study, your decision will not affect any future contact you have with the University of Arizona. An Institutional Review Board responsible for human subjects research at The University of Arizona reviewed this research project and found it to be acceptable, according to applicable state and federal regulations and University policies designed to protect the rights and welfare of participants in research.

V. CONSENT PROCESS

Prospective participants will be informed that their participation is voluntary at the initial conversation about the study by the research team. During the initial conversation, prospective participants will also be informed about the consent process that will take place on the day of the interview or intervention presentation, including the need for the focus group interviews or interventions to be recorded.

The actual consent process will take place on the day of the focus group interview or the day of the intervention presentation (depending on which part the participant is being consented for), before the interview begins, for approximately 20 minutes. The facilitator (the PI, Co-PIs, or community health educator), will hand to each of the participants a written consent form explaining the purpose, procedures, and voluntary nature of the interviews. Since each interview or intervention will be conducted either in English or in Spanish, depending on the participant's language preference, consent forms will be available in English or Spanish (see Informed Consent forms in English). When the consent forms and questionnaires are introduced to them, all participants will be reminded that participation is voluntary and that they may withdraw at any time. The facilitator/CHW will then review the consent form orally as the participants follow along with their copy. The facilitator/CHW will then have participants sign the consent form. An additional copy will be provided to participants to keep for their own records.

Participants in the intervention group will also be informed that agreeing to the study will include signing the consent form along with the Protected Health Information for Research (PHI) form which will allow the University Family Care health plan to provide the research team with the following data for each participant that provides a signed consent and PHI form: 1) Selection and use of a primary care provider; 2) Use of preventive services; and 3) Use of emergency and hospital services.

Immediately prior to the interview, the facilitator will repeat the information verbally that participation is voluntary and that individuals may withdraw or refuse to answer any questions at any point in the study with no effect on their status with the University of Arizona. Of course, all participants will receive and sign consent forms that clearly state the voluntary nature of participation and that they may withdraw themselves at any time (see Informed Consent forms).

VI. STUDY INTERVENTION

Once the health plan analyst randomizes the newly enrolled Medicaid members, potential participants will be contacted by the health plan's call center. A brief verbal overview of the intervention including time requirement and content to be covered will be provided. The potential participants who have been randomly assigned to the intervention group will then be offered the opportunity to set up an individual confidential appointment with a community health worker (CHW) at her earliest convenience.

The call center will provide the research office a list of interested participants and their contact information. Once that list is received by the research office, a CHW will be assigned to each

potential participant. The assigned CHW will call to introduce herself, to answer lingering questions about the intervention and proposed encounter and to confirm the participant's acceptance into the intervention. At that time, the CHW will confirm language and location preference, date/ time of proposed meeting, and the contact information for the research office for any questions.

The intervention will include an initial 50 minute face to face meeting. The CHW will meet with the participant and complete the informed consent process. The participant will be asked to complete a questionnaire at the beginning of intervention presentation performed using a touch tablet device. The questionnaire prior to the presentation will gauge baseline knowledge, patient preferences, informed decision making, and health literacy. Following the questionnaire, there will be a 30 minute intervention presentation. Lately, two boosters follow up call sessions at 2 months and 4 months post initial session.

1. First face-to-face presentation

The appointment will take place in a public location that is convenient for the participant and that is within the locations that have site authorization. These locations include all *county public libraries* and *Pima county health departments*. The initial appointment will take approximately 50 minutes and will include:

- 1.1 Description of the intervention\study
- 1.2 Consenting process
- 1.3 Completion of research surveys\evaluation materials
- 1.4 Half hour presentation and questions

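### Research question 4 asks for an effect of CHW access on informed choice, but the informed-choice survey is described only for women who attend a CHW presentation

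*Protocol*

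**What the plan says.** Section II lists six research questions. Question 4 asks whether access to a CHW improves members' "ability to make informed choices with regard to their use of the healthcare system and own health". It opens in the same way as question 1, which carries the primary outcome.

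Section III sets out the design: "This project will use a mixed qualitative/quantitative pre/post study nested within a randomized controlled effectiveness trial". Newly enrolled women are randomly selected to be invited to a CHW, and "those not selected will constitute the usual care control group".

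The informed-choice measurement is described as follows:

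- **Baseline.** Section IV (Intervention recruitment) states: "This first presentation will include 20 minutes for consent and baseline survey and 30 minutes for the educational content". Section VI says that the questionnaire before the presentation covers informed decision making, among other things, and item 1.3 has the CHW administer it.
- **Consent.** Section V states: "The actual consent process will take place on the day of the focus group interview or the day of the intervention presentation".
- **Month 6.** The recruitment script in Section IV promises a "6-month survey identical to the survey that was completed before the community health worker presentation". Section VII calls this the informed patient choice survey, has a research team member give it by telephone, and links it to baseline by an identifying number.

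Two other survey sources are mentioned. Section III has the health plan supply "other member data including demographic characteristics, medical/pharmacy claims and member satisfaction surveys". Section IV (Focus Group Recruitment) says the focus groups will shape questions for a member satisfaction survey that "will be administered with the potential participants in the next component of the study (e.g., the 1000 planned enrolled participants").

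**The concern.** The question is causal and concerns the factor that is randomised. A reader will expect it to be answered by comparing the invited arm with usual care, as for question 1. The measurement described belongs to a different design: a single group, measured twice, made up of women who were invited, accepted, attended and consented.

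If attenders score better at month 6, the report could present this under question 4 as an effect of CHW access, with the apparent authority of a randomised trial. The data would not support that claim. An analysis plan could narrow the claim, but it could not supply responses from usual-care women if none were collected.

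**Working it through.** No arithmetic applies. The protocol gives no target change, SD or sample-size figure for informed choice. The check is to go through each place where a survey or member contact is described and ask who is surveyed, when, and on what.

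**Step 1. Informed-choice survey points described, by group**

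| Group | First meeting | Month 6 | Total |
|---|---|---|---|
| Invited, attends and consents | 1 (Sections IV, VI) | 1 (Sections IV, VII) | 2 |
| Invited, declines | 0 | 0 | 0 |
| Usual care | 0 | 0 | 0 |

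Section VI offers the appointment to women assigned to the intervention group. Section V places intervention consent on the day of the presentation. A woman who never reaches a presentation therefore has no described consent step or informed-choice survey.

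**Step 2. Could another source fill the two empty rows?**

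- *Health plan data.* Section V lists provider selection and use, preventive services, and emergency and hospital use. Section III adds demographics, claims and satisfaction surveys. None is described as a measure of informed choice.
- *Member satisfaction surveys.* Section III does not limit these by arm, and Section IV gives the 1000 enrolled women only as an example of who will answer. They may reach usual-care women, but nowhere are they said to measure informed choice in that group. Section VII names satisfaction questions separately from the informed-choice survey.
- *Call-center contact.* Section VI has the plan's call center contact potential participants after randomisation. This may reach beyond the intervention arm, but it is described as a short account of the intervention, not a survey.
- *Question 5.* This describes who takes up the offer. It supplies no comparison group for informed choice.

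**Step 3. What can be estimated from what is described?**

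- Invited arm versus usual care: not estimable, because usual care has no measurement.
- Average over all women invited: not estimable, because those who decline have no measurement.
- Change from baseline to month 6 among attenders: estimable.

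**Step 4. What does that remaining change contain?** Besides any CHW effect, it contains:

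- what new members learn about their plan over six months in any case;
- the effect of answering an identical survey twice;
- the change from in-person administration by the CHW (Section VI, item 1.3) to a telephone call from a research team member (Section VII).

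Because attenders select themselves, the change also need not represent all women offered access. Nothing in the described data separates these parts.

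**The case against.** The strongest reply is that Section III openly announces a pre/post component, and that the matched surveys carry it out as labelled. Question 4 names no control group, and questions 5 and 6 plainly do not rest on the randomised contrast, so the list need not be read as six between-arm comparisons. This stands in part: the pre/post design may well be deliberate. But the label does not turn a single-group change into an answer about access, and the protocol nowhere says that question 4 is limited to attenders.

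A second reply is that the study schema and one figure were not available and might show a survey by arm. That is a real limit. The finding rests on the text alone, and the fix allows for it.

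A third is that the protocol blurs its instruments. The recruitment script in Section IV introduces the surveys before and after the presentation as being about satisfaction, while Sections VI and VII describe what appears to be the same survey as one of informed decision making. The reach of the satisfaction survey is also unclear. This shows loose wording, but it does not establish an informed-choice survey of usual-care women.

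A fourth is that the health plan data should not be dismissed as covering consented women only, since the primary outcome and questions 2 and 3 need such data for usual care too. The conclusion does not depend on that restriction: whichever arm they cover, those data are not described as measuring informed choice.

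Finally, question 4 is not primary, and the limits named are common to all pre/post studies. That bears on severity. It does not remove the mismatch between the question and its measurement.

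**Conclusion.** The concern holds. On the text of the protocol, question 4 asks for an effect of CHW access and the described procedures can yield only an uncontrolled change among self-selected attenders. The count is 2 informed-choice survey points for attenders, 0 for usual care and 0 for invited women who decline. The direction and size of any bias cannot be stated from the document.

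This should be corrected, but it is confined to a non-primary question. The primary outcome and questions 2 and 3 are not affected by this point. Confidence is medium, because the schema and one figure were not seen; the conclusion assumes that they contain no informed-choice survey of usual-care women.

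**What to change.** Make two wording changes:

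1. In Section II, restate question 4 as: *change from baseline to six months in informed choice among women who receive the CHW presentation*.
2. In Section III, add: *This component is uncontrolled and will not be reported as an effect of CHW access.*

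If the schema does plan an informed-choice survey of usual-care women, describe that survey in the text instead, with its timing and consent step, and leave question 4 as it is.

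The rewording needs no new data collection and changes no study procedure. Its cost is a weaker claim on a non-primary question.

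### Outcome data for invited women are described as released on signed forms, with no such condition for controls, and the protocol never says that claims for every randomised woman are used

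*Protocol*

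**What the plan says.** **Arms and question.** Section III defines the intervention arm as women chosen at random to be invited to use a CHW, and "those not selected will constitute the usual care control group". The primary question in Section II is "Does access to a CHW improve the likelihood of members identifying a primary care provider and completing a primary care intake visit" within the year. A further question asks how many and which members take up the offer.

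**Order of events.** Section VI: "Once the health plan analyst randomizes the newly enrolled Medicaid members, potential participants will be contacted" by the plan's call centre. Then "The call center will provide the research office a list of interested participants and their contact information". Section IV, Intervention recruitment, describes a CHW call to women who have already agreed: "This first phone call will also include a review and confirmation of study eligibility". The consent and PHI forms are signed at the face-to-face meeting that follows.

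**Release of outcome data.** The recruitment script in Section IV tells women: "The project will also be asking for your permission in the form of signed a Protected Health Information for Research (PHI) to access" plan data on primary care, preventive services, and emergency and hospital use. Section V repeats this for the intervention group: signing lets the plan give the team "the following data for each participant that provides a signed consent and PHI form".

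**The other route.** Section III has a plan analyst set up "health plan claims data pulls, merges and de-identification". It does not say which women these pulls cover. No contact, eligibility call or signature is described for controls.

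**The concern.** The arm definition and the access question need outcomes for all invited women, including those never reached, those who decline and those who do not sign. The only conditions that the protocol states for releasing invited women's outcomes are the signed forms. Controls must reach the comparison by a route without signatures, since none is described for them.

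If the signature condition governs the invited arm, the primary outcome compares women who were reached, agreed, attended and signed with everyone not selected. Such women may differ from the rest in how readily they would see a primary care provider anyway, and that difference would be read as an effect of the CHW. The same applies to the preventive, emergency and hospital outcomes. Who is analysed is commonly left to an SAP, but an SAP can work only with data that the release rule delivers. That is why the point belongs in the protocol.

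**Working it through.** The protocol gives no visit rate, signing share, control-arm size or power calculation, so there is no planned figure to reproduce.

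**Steps that each arm passes through, as described**

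| Step | Invited | Control |
|---|---|---|
| Randomised by plan analyst (VI) | yes | yes |
| Contacted and listed as interested (VI) | yes | none described |
| CHW call with eligibility review (IV) | women who agreed | none described |
| Meeting, consent and PHI forms signed (V, VI) | women who attended | none described |
| Stated basis for outcome release | signed forms (IV script, V) | none stated; the claims pulls in III are the only candidate |

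**Bias if only signers are analysed in the invited arm**

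Let q be the share of invited women who sign, and D the signers' minus the non-signers' intake-visit rate if the CHW has no effect. By randomisation the control rate is q × (signers' rate) + (1 − q) × (non-signers' rate). Subtracting this from the signers' rate gives

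bias = (1 − q) × D.

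Assumed inputs, none from the protocol: no CHW effect, a control rate of 50%, 1000 women analysed per arm, and a two-sided 5% z-test. The rejection probability is Φ(−1.96 + z) + Φ(−1.96 − z), with z = bias / SE. For q = 0.5 and D = 5 points: bias = 0.5 × 5 = 2.5 points; SE = √(0.525 × 0.475/1000 + 0.5 × 0.5/1000) = 2.235 points; z = 1.12; probability = 20.1%.

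| q | D (points, either sign) | Bias (points) | Chance of p < 0.05 with no effect |
|---|---|---|---|
| 0.8 | 5 | 1.0 | 7.3% |
| 0.5 | 5 | 2.5 | 20.1% |
| 0.2 | 5 | 4.0 | 43.3% |
| 0.6 | 10 | 4.0 | 43.3% |
| 0.2 | 10 | 8.0 | 94.9% |
| any | 0 | 0 | 5.0% |

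With a control rate of 30% or 70%, the second row becomes 22.6% to 23.5%. More women make the error rate worse, because the bias stays while the standard error shrinks: at 3000 per arm, q = 0.2 and D = 5 give 87.3% instead of 43.3%.

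**Eligibility call alone**

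If the call removed a share s of women whose visit rate is g points lower than the rest, the bias would be s × g. Assuming s = 1% to 3% and g = 5: 0.01 × 5 = 0.05 to 0.03 × 5 = 0.15 points. This is small beside the signing step. Sex, age and new enrolment should be visible to the plan beforehand, so mainly the ambulatory and community-dwelling criterion in Section IV is left for the call.

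**If all randomised women are analysed as assigned**

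The selection bias is 0. A 10-point effect in users then appears as 10 × q: 8, 5 or 2 points for q = 0.8, 0.5 or 0.2. The number of women needed for the same power rises by about 1/q²: 1.6, 4 or 25 times.

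**The case against.** The strongest case is that the protocol already points the right way. The intervention arm is defined by invitation, not by signing. The uptake question and the planned subgroup analyses of both uptake and outcomes need data on women who decline. Section V is consent language that tells a participant what her signature permits; it does not say that data come only from signers. Control outcomes must arrive without signatures, and nothing shows that this route leaves out invited non-signers. Identifiable data for signers and de-identified claims for everyone could both be true. The PHI authorisation itself, an appendix not available for this review, may settle the matter.

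All of this stands, and it makes a comparison by invitation the more natural intention. It does not close the gap. No sentence says that the de-identified pulls cover invited women who did not sign. Women are also told in the script that access to these data is being asked of them by signature, so using decliners' claims needs cover that is stated in advance.

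Three stronger readings are tempting and should be resisted:

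- *The protocol plans to compare signers with all controls.* It does not say so; this is one possible outcome of an unreconciled text.
- *The eligibility call after randomisation removes women from the trial comparison.* Section IV does not make the call a ground for leaving the comparison; the text goes on to scheduling the presentation.
- *The bias favours the CHW.* The documents give no basis for its sign.

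**Conclusion.** The concern holds as an unreconciled conflict between the arm definition and access question (Sections II and III) and the signature-based release of outcome data (Sections IV and V). If the release rule governs, the randomised comparison is lost for the primary outcome and for the preventive, emergency and hospital outcomes. If every randomised woman's claims are used, nothing is lost.

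Neither size nor sign can be derived from the protocol. The figures of 1 to 4 points, and of a 7% to 43% chance of a false positive finding, rest wholly on assumed signing shares of 20% to 80%, a 5-point gap, a 50% control rate and 1000 women analysed per arm. They illustrate the mechanism and predict nothing for this trial. The point should be settled before claims are requested. Confidence is medium, because the protocol's own wording leans towards comparison by invitation.

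**What to change.** - **Sections III and V, with the script in IV:** state that de-identified claims outcomes, with assigned arm, are delivered for every randomised woman, subject to ethics board approval. State what the signed PHI form covers beyond that, and align the script.
- **Section III:** state that the primary comparison is by assigned arm, whether or not a woman was reached, refused or left a form unsigned.
- **If claims can be had only for signers:** say plainly that the comparison with controls is not as randomised.
- **Minor, Section IV or VI:** state that the eligibility call decides only who receives the presentation and removes no one from the comparison.

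The direct cost is wording and ethics board confirmation. The statistical cost is dilution, since women who decline stay in the denominator; at low uptake the loss of power is large. That is the price of answering the question about access that Section II asks, and a larger sample can offset it, whereas selection bias does not shrink with more women.
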